6. EFFICACY ANALYSES

Unless otherwise stated, all efficacy analyses will be summarized per disease groups (C3G and IgAN) by analysis visit (see Section 13.4). For subjects from the other disease group, all efficacy data will be listed in the listings.

No formal inferential statistics will be applied to data collected in the study.

The following plots with $(\pm SE)$ error bars will be provided for primary and secondary efficacy endpoints outlined below over time based on the analysis visit (see Section 13.4) per disease group:

- Mean with individual subject plots overlaid
- Percentage change from baseline with individual subject plots overlaid

Where applicable, the area for ULN and LLN will be shaded on each graph. Also, the number of subjects contributing to each mean value at a visit will be presented above the x-axis.

In addition, plot with (±SE) error bars will also be provided for percentage change in mean uPCR.

The primary and secondary efficacy endpoint analyses will be performed for both the ITT Population and Per Protocol Population. Exploratory analysis will only be performed for the ITT Population. In addition, when ITT Population is the same as Per Protocol Population, data will only be presented by ITT Population.

Change from baseline are defined as change from Part B baseline and change from Part A + B baseline, which are:

Part A + B baseline: baseline is defined as the most recent non-missing measurement prior to or on the first administration of study drug in Part A (Study Day 1). Baseline can be the same date as first dose, given the measurement is expected prior to first dose when only date information is available.

Part B baseline: baseline is defined as the most recent non-missing measurement prior to or on the first administration of study drug during Part B.

For categorical data, proportions will be based on the number of subjects who have the opportunity to be assessed at that visit.

6.1. Analysis of Primary Efficacy Endpoints

Changes from Part A + B baseline and Part B baseline in proteinuria (24 Hour Urine Collection and mean of triplicate uPCR), percentage changes from Part A + B baseline and Part B baseline in proteinuria will be summarized by visits and by disease groups for both the ITT Population and the Per Protocol Population.

6.2. Analysis of Secondary Efficacy Endpoints

Changes from Part A + B baseline and Part B baseline and percentage change from Part A + B baseline and Part B baseline will be summarized in the same fashion with the primary efficacy endpoints for following endpoints:

Statistical Analysis Plan 2.0 Protocol Number: APL2-201

- eGFR
- Complement biomarkers including serum C3, C3a, C4, C5a, AH50, CH50, and sC5b-9 (see Section 9.1)
- Serum albumin

Additional disease parameters and/or biomarkers may also be analyzed.

eGFR will be calculated using CKD-EPI (2021) formula as:

 $eGFR = 141 \text{ x} \min(SCr/K, 1)^{a} \text{ x} \max(SCr/K, 1)^{-1.209} \text{ x} 0.993^{Age} \text{ x} 1.018 \text{ [if female]x} 1.159 \text{ [if black]}$

where SCr is standardized serum creatinine in mg/dL, K is 0.7 for females and 0.9 for males, a is -0.329 for females and -0.411 for males.

In addition, stabilization or improvement in eGFR from baseline, which is defined as GFR no more than 25% less than the baseline, will be tabulated by analysis visit including the following categories:

- Stable GFR: no more than 25% (+/-) change
- Improvement in GFR: >25% increase
- Worsening of GFR: >25% decrease
- Stabilized or Improved eGFR: <=25% decrease

Complete clinical remission, defined as normalization of proteinuria as defined by < 200 mg/g uPCR, will be tabulated by visit.

In addition, a responder analysis summarizing those patients with uPCR < 500 mg/g by each visit will be provided as well as a responder analysis by visit summarizing those patients with a uPCR reduction from baseline by 30% and 50%. However, subjects who have missing data, or have taken prohibited med, or received dialysis or renal transplant will be identified as non-responder.

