### 12.6. Concomitant Medications

#### 12.6.1. Rescue Antibiotics

Body temperature, vital signs, and relevant blood parameters will be monitored regularly throughout the study to assess for signs of infection. The PI should be contacted immediately in the event of a suspected infection for guidance on appropriate action to be taken. Action to be taken may include administration of a broad-spectrum antibiotic to cover possible resistant organisms such as resistant pneumococcus (eg, levofloxacin).

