#### 14.1.2. Prior and Concomitant Medications

To be eligible for entry into the study, subjects must be on a stable optimized treatment regimen for their disease, in the opinion of the PI, for at least 2 months prior to the first dose of pegcetacoplan (Visit 4), which may include, but is not limited to, use of immunosuppressive agents, antihypertensives and/or antiproteinurics.

All other prior medications administered within 12 Weeks of Screening Visit 3a will be collected.

Use of rituximab, belimumab, and eculizumab during the study (and/or within 6 months prior to the first dose of pegcetacoplan) must be discussed with the sponsor for consideration and approval.

All medications and procedures administered to subjects from the time of informed consent through the End of Study Visit are regarded as concomitant and will be documented.

To the extent possible, baseline treatment regimens (including medications, dietary restrictions, and lifestyle modifications), should not be changed during the study, except as necessary for the well-being of the patient, in the opinion of the PI.

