All protocol deviations will be reviewed and documented before database lock. Protocol deviations will be recorded by the site staff separately from the clinical database. They may also be identified through programmable checks of the data.

Key protocol deviations include any violations of inclusion and exclusion criteria. This includes unknown violations at enrollment and on-study violations, such as taking a prohibited medication.

The CRO/Apellis will classify major and minor protocol deviations per the agreed protocol deviation management plan. The Apellis study team will review the protocol deviations and their classification throughout the study and before database lock.

Number and percentage of subjects with protocol deviation will be tabulated by importance of deviation for Part B and Part A + B, and by disease group for the Safety Population.

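### SAP 6.2 counts users of prohibited medication as non-responders, but nothing supplied defines the term, so a uPCR fall after permitted added therapy can count as response

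*SAP*

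**What the plan says.** SAP 6.2 adds responder summaries to the secondary efficacy analyses: "a responder analysis summarizing those patients with uPCR < 500 mg/g by each visit will be provided", with parallel summaries of subjects whose uPCR fell by 30% and by 50% from baseline. The next sentence sets the exception: "subjects who have missing data, or have taken prohibited med, or received dialysis or renal transplant will be identified as non-responder".

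The idea of a prohibited medication appears in one other place. SAP 5.7 (Protocol Deviations) describes key deviations and adds: "This includes unknown violations at enrollment and on-study violations, such as taking a prohibited medication". It names no drug, class or list.

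The protocol handles concomitant treatment in two places:

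- Protocol 12.6 (Concomitant Medications) has a single subsection, on rescue antibiotics: "Action to be taken may include administration of a broad-spectrum antibiotic to cover possible resistant organisms". It prohibits nothing.
- Protocol 14.1.2 says that baseline regimens, to the extent possible, "should not be changed during the study, except as necessary for the well-being of the patient", as judged by the investigator. It also says that "Use of rituximab, belimumab, and eculizumab during the study", or in the 6 months before the first dose, "must be discussed with the sponsor for consideration and approval". That makes use conditional on approval; it is not a ban.

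Inclusion criterion 5 in Protocol 11.1 accepts immunosuppressive, antihypertensive and antiproteinuric agents as background treatment.

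**The concern.** The rule places prohibited medication beside dialysis and transplant, as events after which a low uPCR is not to be scored as response. Dialysis and transplant can be identified from the data. The medication trigger cannot, because the plan does not say which drugs it covers. Two programmers could flag different subjects and both could claim to have followed the SAP.

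The therapies most likely to lower proteinuria independently of the study drug are those the protocol permits. The study has no control group, so a fall caused by a new or increased background drug cannot be separated from a fall caused by pegcetacoplan. Part B also runs until commercial availability, which leaves a long period in which regimens may change. The responder proportions are descriptive, but the study is meant to establish preliminary efficacy and support further trials, and readers will take these proportions as a measure of drug effect.

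**Working it through.** **Is there a plan figure to reproduce?** Not for this point. The documents give no responder rate and no expected frequency of added therapy. The only sample-size figures are chances of seeing at least one adverse event, 1 − (1 − p)^n. They reproduce (n = 6, p = 0.10 gives 46.9% against the stated 47%; n = 12, p = 0.20 gives 93.1% against the stated figure of more than 93%), but they have no bearing here.

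**Step 1: look for a definition.**

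| Place | What it contributes |
|---|---|
| SAP 6.2 | Uses the term as a trigger; no list or cross-reference |
| SAP 5.7 | Uses it as an example of a deviation; no list |
| SAP 15.1 | Records no changes from the protocol's analyses, so adds no list |
| Protocol 12.6 | Rescue antibiotics only |
| Protocol 14.1.2 | Conditional permission for three named drugs; regimen changes discouraged but allowed when needed |
| Protocol 11.1 and 11.2 | Eligibility; no list of drugs barred during treatment |

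None gives the trigger any content.

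**Step 2: follow one subject through the rule.** Suppose a Part B subject has an antiproteinuric increased, or an immunosuppressive started, because the investigator judges it necessary. uPCR then drops below 500 mg/g or falls by 30% or 50%.

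- Missing data: no.
- Prohibited medication: no, since the change was permitted.
- Dialysis: no.
- Transplant: no.

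The subject is a responder. The same holds for rituximab, belimumab or eculizumab given with approval.

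**Step 3: check whether the analysis sets remove the subject.** Under SAP 4.2 the ITT set equals the safety set: everyone who rolls over and receives at least one 1080 mg dose. Added therapy does not exclude anyone. Under SAP 4.3 the per-protocol set removes subjects with deviations that could influence efficacy, but a change the protocol allows is not clearly a deviation.

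**Step 4: size.** Moving one subject from responder to non-responder changes a group proportion from r/n to (r − 1)/n, a shift of 100/n percentage points. Protocol 16.1 plans 6 to 12 subjects per disease. Part B includes only those who roll over, and that number is not stated.

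| n in group | Shift per subject (points) |
|---|---|
| 12 | 8.3 |
| 10 | 10.0 |
| 8 | 12.5 |
| 6 | 16.7 |
| 4 (assumed low roll-over) | 25.0 |
| 3 (assumed low roll-over) | 33.3 |

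**Step 5: what a remedy has to handle.** SAP 13.3 defines two baselines, one before the first dose in Part A and one at the start of Part B. A drug added during Part A is new relative to the first but already part of the regimen at the second. A therapy trigger must therefore name its reference regimen. Because Part B is open-ended, it must also say how long before a visit a change counts.

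**The case against.** Several counter-arguments have force.

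- **Most of the rule works.** A reader might infer that the non-responder rule never operates. That goes too far: missing data, dialysis and transplant need no list. Only the medication trigger is undefined.
- **The trigger may not be wholly empty.** Use of rituximab, belimumab or eculizumab without approval would breach Protocol 14.1.2 and could be read as prohibited, as could an unjustified regimen change. This stands, but the SAP does not say so, and approved or justified use still escapes.
- **A list may exist elsewhere.** SAP 5.7 sends deviation classification to a separate management plan, and parts of the protocol appendices are not in the text supplied. So the supportable statement is that no list appears in that text, not that none exists. Protocol A1.1 refers anything not described there back to the main protocol, which makes a hidden Part B list unlikely. If the list sits in the deviation plan, the SAP should cite it.
- **The per-protocol analysis and the listings help.** They do in part. Unapproved use might be removed, and the SAP 5.4 listing with individual plots lets a reader trace treatment in small groups. Neither changes the ITT proportions, and the per-protocol tables are dropped when the two sets coincide.
- **Counting response regardless of permitted therapy is a legitimate choice.** It is, and the SAP does not say that it intends otherwise. The added trigger is therefore a change of strategy as well as a repair of wording, which is why both versions should be shown.
- **The consequence is limited.** These responder cut-offs are not among the endpoints in Protocol 9.2, and there is no formal inference. No test, error rate or decision rule is affected.

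**Conclusion.** The point holds in a bounded form. One of four non-responder triggers in SAP 6.2 has no defined content in the text supplied. As written, permitted added or increased proteinuria-lowering therapy does not prevent a subject from counting as an ITT responder, and with no control group that can credit another treatment's effect to pegcetacoplan. It should be settled before database lock.

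The effect is 100/n points per affected subject: 8.3 to 16.7 over the planned 6 to 12 per disease, and more if roll-over into Part B is low. This assumes at least one such subject and a uPCR value that meets the cut-off. The documents give no frequency, so no total can be stated.

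A reader might also infer that the reported rates are bound to be inflated. The documents do not support that. Nothing shows that any subject added therapy, and one who did may also have responded to the study drug. What is certain is narrower: adding a therapy trigger can only lower a proportion or leave it unchanged.

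**What to change.** Amend SAP 6.2 before database lock:

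1. Keep the prohibited-medication trigger, but define it there or cite the document that holds the list.
2. Add a non-responder trigger: a new start or dose increase of an immunosuppressive or antiproteinuric agent (including ACE inhibitors and angiotensin-receptor blockers), or receipt of rituximab, belimumab or eculizumab.
3. Judge it against the regimen at the baseline used for that analysis (Part A + B or Part B), within a pre-specified look-back period before each visit, so that a brief course does not fix non-response for the whole extension.
4. Have the classification made without sight of uPCR results.
5. Report responder proportions with and without the added trigger.

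The cost is SAP wording, a medication review and one repeated set of tables. Concomitant medications are already collected through Part B and classified under SAP 5.4. The documents do not say whether every dose change is recorded, so that should be confirmed first. The drawback is that some subjects whose therapy changed for unrelated reasons become non-responders; showing both versions makes this visible. The change concerns how data are classified, not which treatments patients may receive.

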6.3. Analyses of Exploratory Endpoints

Changes and percentage of changes from Part A + B baseline and Part B baseline will be summarized by visits using both the ITT Population and PP Population for the following disease specific biomarkers:

- IgAN: autoantibodies to Gd-IgA1 and antiglycan antibodies
- LN: autoantibodies to dsDNA, C3 and C1q (listing only)
- C3G: C3 nephritic factor (C3NeF)

Additional disease parameters and/or biomarkers may also be analyzed.

Finally, the time to the composite clinical outcome will be summarized by disease group using Kaplan-Mier (KM) method. The detail of definition and search criteria is provided in the following table:

Composite clinical outcome category	Definition	Search criteria	
Doubling of serum creatinine	Doubling of the serum creatinine level from Part A baseline sustained for at least 30 days	Search post-baseline creatinine that is twice of Part A baseline, and the following assessment that is >=30 days away and is also twice of baseline; if 2nd assessment is missing but the subject discontinues treatment after 1 st doubling creatinine, this is also counted as an event. Any local lab can also be used for confirmation. Only assessments on or before treatment discontinuation will be used.	
Disease progression	Treatment discontinued due to disease progression	Search treatment discontinued reason due to disease progression	
Progression to chronic kidney disease stage 5	An estimated GFR of <15 ml per minute per 1.73 m2 confirmed by a second measurement after ≥30 days	Search for eGFR<15/min/1.73m2, and the following assessment that is >=30 days away and is also<15/min/1.73m2; if 2nd assessment is missing but the subject discontinues treatment then it is also counted as an event. Any local lab can also be used for confirmation. Only assessments on or before treatment discontinuation will be used.	
End-stage renal disease	Onset of end-stage kidney disease (defined as maintenance dialysis for ≥30 days)	Search concomitant procedure for dialysis and check (End Date-Start Date)>=30	
Kidney transplantation	Kidney transplantation	Search concomitant procedure for transplantation	
Death	Death from renal or cardiovascular causes	Search death with cause related to renal or cardiovascular	

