## 9.2.3. Exploratory Endpoints

- Complete renal response: defined as <200 mg/g uPCR and stabilization or improvement in eGFR from baseline to Week 48
- Changes of disease-specific biomarkers:
  - LN: autoantibodies to double-stranded DNA, C3, and C1q
  - Primary MN: autoantibodies to PLA2R
  - C3G: C3NeF (Part A only)

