Visit Window (±Days)	2	2	2	2	7	7	7	NA
$Pegceta coplan\ administration^{b,f}$	X	X	X	X	X	X	X	
Injection site assessment g	X	X	X	X	X	X	Х	
Concomitant medications	X	X	X	X	X	X	Х	X
Vital sign measurementsh	X	X	X	X	X	X	Х	X
Urine								
24-hour Urine Collection i	X					Xi	Xi	X
Dispense uPCR containers	X		X	X	X	X	Х	
Return uPCR samples j			X	X	X	X	Х	
Urinalysis—microscopic & Dipstick k	Х	Х	X	Х	X	Х	х	Х
Blood 								
Pharmacokinetic Sample Collection m	Х	Х	Х	Х	X	Х	х	Х
Antidrug Ab assays n	X			X		Х	X n	X
Hematology and chemistry 0,p	X	X	X	X	X	X	Х	X
PD for Complement profile	X	X	X	X	X	X	Х	X
Pregnancy (β-HCG and FSH)	X							
Disease-Specific Biomarkers	X							X
eGFR q	X							X
Urine pregnancy test r	X			X	X	X	Х	
Adverse events	X	X	X	X	X	X	х	Х
Drug Dispensation for Home Administration	X	Х	Х	Х	X	Х	Х	

Abbreviations: Ab = antibodies; ACR = albumin-to-creatinine ratio; ADA = antidrug antibody; ALP = alkaline phosphatase; ALT = alanine aminotransferase; aPTT = fibrinogen activated partial thromboplastin time; AST = aspartate aminotransferase; β-HCG = beta human chorionic gonadotropin; BUN = blood urea nitrogen; CKD-EPI = Chronic Kidney Disease Epidemiology Collaboration; ECG = electrocardiogram; eGFR = estimated glomerular filtration rate; ETE = Early Termination Exit Visit; ETF = Early Termination Follow-up Visit; FSH = follicle-stimulating hormone; GGT = gamma-glutamyl transferase; INR = international normalized ratio; LDH = lactate dehydrogenase; PCR = protein-to-creatinine ratio; PD = pharmacodynamics; PI = primary investigator; PK = pharmacokinetics; RBC = red blood cell(s); SC = subcutaneous;

uACR = urine albumin-to-creatinine ratio; uPCR = urine protein-to-creatinine ratio; WBC = white blood cell(s); WOCBP = women of childbearing potential.

- a Subjects who discontinue treatment early should complete one ETF 6 weeks after discontinuation of treatment and one ETE Visit 6 weeks after the ETF.
- b If subjects have not transitioned to twice-weekly dosing before entry into Part B, then transition visits T1, T2, and T3 need to be scheduled. Patients who had transitioned to twice-weekly dosing prior to entry into Part B may omit the Part B dose transition visits.

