1. INTRODUCTION

This statistical analysis plan (SAP) describes detailed statistical methods to be used for analysis and data presentation for reporting safety and biologic activity data of investigational infusion of APL-2 for Apellis study protocol APL2-201 for Part B only.

The planned length of participation in the study Part A (Core Study Phase) for each subject is 76 weeks, including an approximate 4-week screening period, 48-week treatment period and 24-week follow-up period. Following Day 336 and the completion of Part A, any subject who, in the opinion of the investigator, is experiencing clinical benefit from APL-2 administration will be invited to participate in Part B, a Long-Term Extension Phase in order to continue to receive treatment with APL-2 until it is commercially available for the disease under treatment. If invited to participate in Part B, the subject can enter the Long-Term Extension Phase as soon as they complete the 48-week treatment period and do not need to participate in the 24-week follow-up period.

Statistical Analysis Plan Version 1.0 was used to produce the Part A (Core Study Phase) analysis. This SAP will present the results for the final analysis for subjects who rolled over into Part B, presenting the safety and efficacy results of Part B (Long-Term Extension Phase) and Part A + B as Part B subjects in Part B data and as well as Part A data. Definitions for the study days and baselines are outlined in Section 13. This document has been prepared according to study protocol amendment 7.0 dated 07 July 2022.

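### SAP 6.3 plans by-visit Part B changes in disease-specific biomarkers, but protocol Table A1 schedules no on-treatment draw after the Part B baseline

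*SAP*

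**What the plan says.** The SAP describes itself as written "for Apellis study protocol APL2-201 for Part B only", reporting Part B and Part A + B. Section 6.3 sets the exploratory biomarker analysis: "Changes and percentage of changes from Part A + B baseline and Part B baseline will be summarized by visits". Three disease groups follow. IgAN reads "IgAN: autoantibodies to Gd-IgA1 and antiglycan antibodies". C3G has C3NeF with no restriction by study part. LN is for listing only. Primary MN is absent, although protocol Section 9.2.3 still names "Primary MN: autoantibodies to PLA2R".

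Protocol Appendix 1, Section A1.1.2, refers to Table A1 for the procedures at each Part B visit. The row "Disease-Specific Biomarkers" in that table is marked in two columns: Week 48 (Visit 15) and the combined early-termination column. Footnote a gives the timing of the latter: "Subjects who discontinue treatment early should complete one ETF 6 weeks after discontinuation of treatment and one ETE Visit 6 weeks after the ETF".

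**The concern.** A by-visit change from the Part B baseline needs a baseline value and at least one later value on treatment. Table A1 supplies the first but schedules none of the second. The only later draws that it provides come from subjects who have stopped drug.

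Two outcomes are possible if the SAP is followed as written. Where no sample is drawn, the Part B rows are empty. Where an early-termination sample exists, the visit-window rules can place it under a treatment visit, so an off-drug value from a subject who stopped would stand among changes during long-term treatment.

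**Working it through.** No power, alpha or sample-size figure bears on this point. The check counts the scheduled draws and applies the SAP's window rules.

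**1. Draws in Table A1.** The table has 8 columns. Removing Week 48 (baseline) and ETF & ETE (off drug) leaves 8 − 2 = 6 on-treatment columns after baseline.

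| Row | Week 48 | T1 | T2 | T3 | Week 60 | Week 72 | Week 84 on | ETF & ETE | On-treatment, after baseline |
|---|---|---|---|---|---|---|---|---|---|
| Disease-specific biomarkers | X | – | – | – | – | – | – | X | 0 of 6 |
| Antidrug antibodies | X | – | – | X | – | X | X | X | 3 of 6 |
| Complement profile | X | X | X | X | X | X | X | X | 6 of 6 |
| Hematology and chemistry | X | X | X | X | X | X | X | X | 6 of 6 |

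The other rows fit their own footnotes (antidrug antibodies and physical examination every 24 weeks from Week 72), so misaligned columns are unlikely to explain the blanks.

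**2. Week 48 is the baseline.** SAP 13.3 takes the last value on or before the first Part B dose, and SAP 13.4.3 maps Visit 15 to Part B Day 1. The Week 48 draw therefore gives no change from Part B baseline.

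**3. Timing of the remaining draws.** ETF falls 6 × 7 = 42 days after stopping and ETE 12 × 7 = 84 days after. That is at most 2 scheduled values per subject, from early stoppers only.

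**4. C3NeF.** Protocol 9.2.3 and 16.2.2.3 restrict it to Part A, and SAP 5.2.3 repeats the restriction. SAP 6.3 omits it. No C3NeF value is expected after Part A, including at ETF or ETE.

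**5. Window mapping for the other markers.** SAP 13.4 assigns every post-baseline record to an analysis visit. The Part B windows in 13.4.3 run without a gap from Day 2 and contain no ETF or ETE row. Take a subject who stops on Part B Day 84:

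- ETF day = 84 + 42 = 126; ETE day = 126 + 42 = 168.
- The Week 24 window is Day 126 to before Day 210, with or without transition visits in Part B. Both records fall in it.
- Window midpoint = (126 + 210) / 2 = 168. Distances are 168 − 126 = 42 for ETF and 168 − 168 = 0 for ETE.
- The closest-to-midpoint rule selects ETE. The reported Week 24 change is a value taken 168 − 84 = 84 days after stopping.

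**6. What can still be derived.** Protocol Table 1 schedules these biomarkers at every Part A treatment visit. Visits 5 to 15 give 11 post-baseline time points, Week 2 to Week 48, for change from the Part A + B baseline.

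**The case against.** The strongest reply is that little is at stake. The markers are exploratory, the SAP applies no inferential statistics, and a row with no subjects is visible and misleads nobody. That stands for C3NeF, where the Part B rows would simply be empty. It does not answer the mapping problem, where a number appears under the wrong visit.

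A second reply concerns the IgAN antibodies. The protocol's exploratory endpoints do not name them, so the generic Table A1 row may not cover them. That also stands: the two off-drug values are an upper limit, and if the row does not cover these antibodies, Part B has no scheduled value for them at all. A reader might go further and call them an undeclared endpoint, since SAP 15.1 reports no change from the protocol. The documents give that little support. Protocol 16.2 and 16.2.2.3 allow further analyses and biomarkers, and SAP 15.2 says that modified Part A endpoints are used for Part B. Naming the markers in 15.1 is a minor clarification.

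A reader might also infer that on-treatment Part B samples do not exist. The documents show only that Table A1 schedules none. Protocol 13.4.2 permits unscheduled visits with any listed procedure, and Appendix 2 was not in the text reviewed. Ad hoc draws would still not support a planned by-visit summary.

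**Conclusion.** The mismatch holds. For the biomarkers in SAP 6.3, 0 of 6 on-treatment Part B columns after baseline have a scheduled draw, so no scheduled on-treatment change from the Part B baseline can be derived. The summaries affected are IgAN and C3G. For C3G, the SAP conflicts with the protocol and with its own Section 5.2.3. For IgAN, an off-drug value would be reported as a treatment visit if the Table A1 row covers those antibodies, at least one IgAN subject stops early in Part B, and the window rules are applied as written.

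Two wider readings are not supported. A reader might expect the C3G table to fill with washout values, but C3NeF is restricted to Part A, so none is expected. A reader might also extend the gap to complement markers, serum albumin or eGFR, because SAP 2.1.1 uses the biomarker label for some of these and the Table A1 eGFR row is equally sparse. The complement profile and chemistry are drawn at every Part B visit, and SAP 6.2 calculates eGFR from serum creatinine.

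This should be corrected before the Part B tables are produced, but no primary, secondary or safety result depends on it.

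**What to change.** In SAP 6.3:

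- Remove the Part B-baseline and Part B-visit summaries for these biomarkers.
- Limit the change tables to Part A visits through Week 48, against the Part A + B baseline.
- Mark C3NeF as Part A only, in line with SAP 5.2.3.
- Show ETF and ETE values only in listings labelled post-treatment, and state in SAP 13.4 that they are excluded from the visit windows.
- As a minor addition, name the IgAN antibodies in SAP 15.1.

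If Part B samples were in fact drawn, Table A1 and the SAP must be reconciled instead.

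The cost is SAP wording and one fewer exploratory Part B table, which the scheduled data could not fill with on-treatment values.
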